6.2. Specific Objectives

To compare:

1. The bleeding on probing (BoP) between the group with *Lactobacillus reuteri* probiotic application after root surface debridement (RSD) with group of mechanical debridement alone at 3 months.
2. The probing pocket depth (PPD) between the group with *Lactobacillus reuteri* probiotic application after root surface debridement (RSD) with control group of mechanical debridement at 3 months.
3. The clinical attachment level (CAL) between the group with *Lactobacillus reuteri* probiotic application after root surface debridement (RSD) with control group of mechanical debridement at 3 months.
4. The plaque index (PI) between the group with *Lactobacillus reuteri* probiotic application after root surface debridement (RSD) and control group with mechanical debridement at 3 months.

5. The gingival index (GI) between the group with *Lactobacillus reuteri* probiotic application after root surface debridement (RSD) and control group with mechanical debridement at 3 months.

7. Scope and Limitations

This study will focus on the applications of *Lactobacillus reuteri* probiotic as local delivery agent in management of periodontitis. This agent will act as an adjunct in non-surgical periodontal therapy and will be applied subgingivally into the pocket after root surface debridement procedure. This new invention using probiotics will give advantages in this field. However, there are certain limitations that might affect the outcome of this study. For example, it is impossible to draw any firm conclusions, given the wide variety of delivery vehicles (liquid drops, lozenges, powder etc.).

8. Rationale of Study

To date, effectiveness of local drug delivery as an adjunct has been proven (Tan et al., 2020), but studies regarding effectiveness of probiotic as an adjunct is still lacking. There has been no study conducted specifically focusing on the effectiveness of *Lactobacillus reuteri* probiotic as an adjunct in subgingival debridement clinically for patients with type 2 diabetes mellitus. In the past decade, there has been a growing interest in utilising probiotics to improve periodontal health. Initially, experimental studies in animal models explored the use of *Lactobacillus spp.* and *Bifidobacterium spp.*, revealing a reduction in periodontitis (Teughels et al., 2007). Subsequent studies investigated the

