10.2. Sample Size Calculations

Sample size calculation done using G-power sample size calculator version 3.1.9.6 (Kang, 2021). The sample size calculation is based on the previous study by Minić and colleagues on the effect of the local probiotics in the therapy of periodontitis: a randomised prospective study (Minić, Pejčić, & Bradić-Vasić, 2022). The statistical test was set as “means: difference between two independent means (two groups)”, with an alpha error of 5%, and 90% statistical power. The minimum total sample size required is 12. Considering the probability of drop out rate 10%, 14 patients will be included.

$$\underline{12 + (12 \times 0.10) = 14}$$

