10.4. Study Design

This is a single blinded, prospective, randomised split-mouth clinical trial, where quadrants will be divided randomly into control and test groups.

Baseline records of periodontal clinical parameters will be taken for all subjects which include; bleeding on probing index (BoP), probing pocket depth (PPD), clinical

attachment level (CAL), plaque index (PI) and gingival index (GI). All the clinical records will be kept in locked case and delivered after the end of the clinical trial. University of North Carolina (UNC-15) probe will be used to measure the periodontal pocket depth and CAL.

All patients, after the baseline parameters recorded, will then receive motivation and oral hygiene instructions on standard effective oral hygiene practice which include tooth brushing, flossing, interdental brush usage and single tufted brush, followed by full mouth root surface debridement (RSD) under local anaesthesia on all teeth with pocket of ≥ 5 mm (Heitz-Mayfield, 2005; Matesanz-Pérez et al., 2013) using ultrasonic scaler and Gracey's curette, until the root surface feels smooth and clean to an explorer tip of UNC-15 probe (Kaner et al., 2007). For each patient, complete full mouth professional mechanical plaque removal (PMPR) and RSD will be done within 24 hours. All these will be done by main examiner, [name].

Both right (quadrant 1 and 4) and left (quadrant 2 and 3) halves will be assigned randomly to one of the two treatment modalities. A simple randomisation method will be employed to assign 14 participants into two groups (Group 1 and Group 2 corresponding to right halves: test and left halves: control or right halves: control and left halves: test) alternatively. A series of fourteen unique random numbers will be generated using the Numbers RAND() formula, one for each. Patients will then be alternately assigned to Group 1 and Group 2, starting with Group 1, done by supervisor, [name]. The treatment allocation cards will be sealed in envelopes until the clinical procedure.

The subgingival applications of either control (sterilised distilled water) or test (*Lactobacillus reuteri* probiotic) drops will be done based on the randomisation sequences done by [name] before. The allocated group for every subject will only be told to [name] on the

[figure not shown]

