10.9. Study Flow Chart

11. Statistical Analysis

All data will be collected in numerical form and will be analysed using the IBM SPSS Statistics Version 26.0 software. Histogram plot of data will be first used to check for normality of data distribution. Then, either Independent t-Test or Mann-Whitney Test will be used to compare data between two groups. The variables will be presented as mean and standard deviation for parametric test or median and interquartile range for non-parametric test. Significant level will be set at p-value $p < 0.05$. Meanwhile data within groups to evaluates statistically significant changes from baseline to follow up visits will be analysed either using Paired t-Test or Wilcoxon Signed Ranked Test.

Parameter	Visit	Control group	Test group	p-Value
BoP	Baseline			
	3 months			
PPD (mm)	Baseline			
	3 months			
CAL (mm)	Baseline			
	3 months			
PI	Baseline			
	3 months			
GI	Baseline			
	3 months			

Clinical Parameters for Groups 1 and 2 (mean \pm SD or median (IQR)) at different time intervals

(*denotes statistically significant difference, $p < 0.05$)

12. Budget

	Quantity	Cost/ Unit	Total Cost
Disposable syringe (1ml) (100's/ box)	1	RM 50.00	RM 50.00
Flexible tip (0.25mm) (100's/ box)	1	RM 200.00	RM 200.00
Gracey curettes	28	RM 209.25	RM 5859.00
Sharpening kit	1	RM 2442.00	RM 2442.00
Small cassette	3	RM 592.50	RM 1777.50
Lactobacillus reuteri probiotic	20	RM 134.50	RM 2690.00
Acrylic stents	20	RM 200.00	RM 4000.00
Oral hygiene kit	20	RM 100.00	RM 2000.00
		T O T A L COST	RM 19,018.50

13. Gantt Chart

	2023	2024				2025				2026			
	NOV- DEC	JAN- MAR	APR- JUN	JUL- SEP	OCT- DEC	JAN- MAR	APR- JUN	JUL- SEP	OCT- DEC	JAN- MAR	APR- JUN	JUL- SEP	OCT- DEC
Drafting proposal													
Defence of research proposal (DRP)													
Ethics application													
Data collection preparation													
Data collection													
Thesis write-up													
Submission research paper													
Thesis submission for viva													
Research sends for publication													

14. References

- Chandran, Arunah. (2020). National Diabetes Registry Report, 2013-2019. Ministry of Health Malaysia. https://www.moh.gov.my/moh/resources/Penerbitan/Rujukan/NCD/Diabetes/National_Diabetes_Registry_Report_2013-2019_26082021.pdf

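### The test-versus-control comparison at 3 months ignores the recorded baseline, which enters only through within-half before-after tests and an implied baseline p-value

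*Combined protocol and SAP*

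**What the plan says.** Section 10.4 states that "Baseline records of periodontal clinical parameters will be taken for all subjects", and lists BoP, PPD, CAL, PI and GI. The objectives in section 6.2 compare the probiotic halves "with control group of mechanical debridement at 3 months", which points to a comparison of 3-month levels.

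Section 11 names two analyses. Between groups, it plans an independent t-test or a Mann-Whitney test. Within groups, it plans a paired t-test or a Wilcoxon test on "data within groups to evaluates statistically significant changes from baseline to follow up visits". The empty results table has a baseline row and a 3-month row for each parameter, a column for each group, and one p-value column. It has no row for change, no adjusted difference and no confidence interval. Neither a baseline covariate nor a between-half comparison of change appears anywhere.

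Sections 10.4 and 10.7 give full-mouth debridement to both halves. The halves then differ only in the drops applied.

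**The concern.** Two things are at stake.

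The first is inference. Both halves are expected to improve because both are debrided. Change in the control half reflects debridement, oral hygiene and the water drops. Change in the test half reflects the same plus any probiotic effect. A significant change in one half beside a non-significant change in the other is not a test of the difference between them, yet the plan puts those p-values next to the between-group one.

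The second is the between-half estimate itself. In a trial this small the two halves can differ at baseline by chance. If halves that start deeper also tend to end deeper, part of that difference reappears at 3 months. Randomisation removes it on average over repeated trials, but not in the one trial that is run. The data needed to correct for it are already being collected.

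**Working it through.** **The plan's own figures.** Section 10.2 sizes the trial "with an alpha error of 5%, and 90% statistical power", then states that "The minimum total sample size required is 12" and adds 10% for dropout: 12 + 1.2 = 13.2, rounded up to 14. That step reproduces. The 12 cannot be checked, because no effect size or SD is given; the text says only that "The sample size calculation is based on the previous study" it names. The effect sizes and correlations below are therefore assumptions.

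**Precision.** Let r be the correlation, across patients, between the baseline and the 3-month half difference. Relative to a paired test without baseline, the regression multiplies the variance of the estimate by about (1 − r²) × (1 + 1/(n − 3)). The second factor is the small-sample cost of estimating the slope. At n = 12 it is 1 + 1/9 = 1.111. Power comes from the noncentral t distribution, two-sided 5%, at an assumed standardised paired difference dz = 0.8.

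Unadjusted, n = 12: noncentrality 0.8 × √12 = 2.77, 11 df, power 71%.

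Adjusted, n = 12, 10 df:

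| r | Variance factor | Noncentrality | Power |
|---|---|---|---|
| 0 | 1.111 | 2.77/√1.111 = 2.63 | 66% |
| 0.3 | 0.91 × 1.111 = 1.011 | 2.76 | 70% |
| 0.5 | 0.75 × 1.111 = 0.833 | 3.04 | 78% |
| 0.7 | 0.51 × 1.111 = 0.567 | 3.68 | 91% |

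With 14 pairs, power is 79% unadjusted and 75%, 79%, 86% and 96% adjusted. Direct simulation of the regression agrees to within about one point. The variance breaks even where (1 − r²)(1 + 1/(n − 3)) = 1, that is at r = 0.32 for n = 12 and r = 0.29 for n = 14.

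**Chance imbalance.** Let c be the correlation between the two halves at baseline. The mean baseline half difference then has SD √(2(1 − c)/n) in outcome SDs. With c = 0.5 and n = 14 this is √(1/14) = 0.27, a 95% range of about ±0.52. For c from 0.3 to 0.7 the range runs from ±0.62 to ±0.41. Simulation (c = 0.5, n = 14, no treatment effect, equal spread at both visits so that the slope equals r) looked at the tenth of trials with the largest imbalance. The unadjusted 3-month difference was off by about 0.16, 0.28 and 0.39 SD at r = 0.3, 0.5 and 0.7. The adjusted estimate was off by about zero.

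**Within-half p-values.** Suppose there is no probiotic effect, 14 patients, and each half improves by 0.8 SD of its own change (assumption). Each within-half test then has 79% power. If the halves were independent, the test half would be significant and the control half not in 0.79 × 0.21 = 17% of trials. With a correlation of 0.5 between halves, simulation gives 12%. A valid two-sided 5% comparison would favour the probiotic falsely in 2.5%. The contrast is smaller, 5 to 6%, if each half improves by 1.0 SD.

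**Coding the covariate.** The intercept is the adjusted effect only if the baseline difference is entered as it stands, so that zero means no baseline difference. If its sample mean is subtracted first, the intercept becomes the raw 3-month mean difference, paired with a standard error that is too small. Under no effect with 12 pairs, simulated type I error is then about 8% at r = 0.5 and 14% at r = 0.7, against 5% uncentred.

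**The case against.** The strongest objection is that the precision gain cannot be shown from the documents. They give no r, and the r that matters is between within-patient differences. Differencing removes the stable patient component and leaves proportionally more probing error (PPD is read to the nearest mm), so a low r is plausible. A reader might infer that adjustment is certain to sharpen the comparison. It is not: below about 0.3 it gains nothing and can lose a little. This objection stands, and it makes the gain conditional.

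A reader might also take 71% as the power of the planned analysis. It is not. It belongs to a paired test between halves, which the plan does not contain.

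Nor do the documents support calling the unadjusted contrast biased, since randomisation of halves makes it correct on average. They also do not support predicting a false claim: the objectives are between-group, and nothing says that efficacy will be judged from within-half tests. The simulated 12 to 17% shows how misleading that reading would be, not that it is planned.

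Finally, the baseline p-value is inferred from the layout of an empty table, and section 11 does not say outright whether levels or changes are compared. The table and the objectives point to levels.

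None of this removes the core fact: no planned analysis compares the halves while allowing for their baseline.

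**Conclusion.** The point holds as a recommended improvement, not as a fatal flaw. The omission is plain from section 11. Correcting for whatever baseline imbalance occurs, and keeping efficacy claims off within-half p-values, are justified whatever the exact value of r. The gain in power is not assured: it ranges from a loss of about 5 points (r = 0) to a gain of about 20 points (r = 0.7) at the assumed dz = 0.8 with 12 pairs, measured against a paired test without baseline. Moving from the planned independent-groups test to a within-patient analysis is a separate matter, which the regression also addresses.

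**What to change.** - Pre-specify, as the main analysis of each parameter, a regression of the within-patient 3-month difference (test half minus control half) on the within-patient baseline difference. Enter the covariate uncentred and say so. Report the intercept, the treatment effect at zero baseline difference, with its 95% CI.
- Define half-mouth scores. Section 10.6 defines BoP, PI and GI per individual, so they must be rebuilt from the tooth scores of each half. State likewise how site-level PPD and CAL are averaged within a half.
- State in advance what will be done if residuals are plainly non-normal. The present plan has a rank-test route, and the regression alone does not.
- Report within-half changes descriptively. Base no efficacy claim on within-half p-values or on a baseline p-value.

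The cost is a change of wording and one regression per parameter in the SPSS software already planned, with no new data. The statistical price is one degree of freedom, and about 5 power points if baseline turns out to be unrelated to outcome. The choice has to be fixed before the data are seen.
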